Various studies have evaluated the outcomes of different closure devices, however, there are no reports assessing the length of closure times using DERMABOND PRINEO (Ethicon, Johnson and Johnson, Somerville, New Jersey) Knotless Tissue Control Devices during superficial closure in orthopaedic surgery. Huemer et al.(1) performed an observational study of 180 patients who had 224 excisional body-contouring surgeries utilizing Dermabond Prineo for superficial closure. Authors concluded that this closure type enables the surgeon to perform a quick and smooth skin closure. However, 4 patients (1.8%) developed local allergic reactions, which necessitated early removal and topical corticosteroid treatment. Parvizi et al.(2) performed an open, prospective, randomized clinical study of superficial wound closure on 60 patients undergoing abdominoplasty with either Dermabond Prineo or conventional superficial closure. They found significantly lower price (\$134.79 cheaper) and significantly better Hollander Cosmesis Scale scores in Dermabond Prineo cohort. In addition, there was a significantly better cosmetic outcome at 6 and 12 months after surgery. The use of Dermabond Prineo may be able to decrease operative time and costs in other surgical fields, such as orthopedics. Careful patient allergy history is necessary to avoid adhesive allergic reactions.

Regulatory Sponsor:

This study is an Investigator Initiated research trial. Each study site will be considered its own regulatory sponsor and is responsible for internal data monitoring and any study reporting required by ClinicalTrials.gov.

Study Design:

In this prospective pilot study examining the superficial closure during total knee arthroplasty, active subjects will receive the STRATAFIX Spiral Knotless Tissue Control Device for subcuticular closure in addition to DERMABOND PRINEO (Ethicon, Johnson and Johnson, Somerville, New Jersey) system for dermal closure. The control subjects will receive staples (standard-of-care).

The purpose of this study is to compare end points (see below):

- **The primary endpoint of the study** will be cosmesis observation using the modified Hollander scale (Table1).
- **Secondary endpoints** will examine: wound closure time, patient satisfaction with wound appearance, wound related complications, cost comparison including time and materials

As a pilot study, hypothesis testing will not be performed.

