Post-operatively, patients will be assessed at clinic visits at 6 weeks and 3 months. At these time points, we will assess (**Table 2**):

- Incidence of any wound complications
- Wound appearance using the Hollander cosmesis questionnaire (**Table 1**)
- Patient satisfaction with wound appearance using visual analogue scale (VAS)

Table 1. Hollander cosmesis questionnaire	
Stepoff borders	0 for yes, 1 for no
Contour irregularity – puckering	0 for yes, 1 for no
Scar width – greater than 2mm	0 for yes, 1 for no
Edge inversion – sinking, curling	0 for yes, 1 for no
Inflammation – redness, discharge	0 for yes, 1 for no
Overall cosmesis	0 = poor, 1 = acceptable

Table 2: Research Procedures				
REQUIRED STUDIES	Pre-Op	Intra-operative	6 weeks post-op	3 months post-op
Informed Consent	x			
Length of surgery		x		
Length of closure time		x		
Amount of suture material used		x		
Surgeon experience level		x		
Incidence of wound complications			x	x
Hollander cosmesis questionnaire			x	x
Patient satisfaction with wound appearance (VAS)			x	x

Methods

- A prospective randomized pilot study

Sample

- 60 subjects for a pilot study

Inclusion Criteria:

1. Males and females, between the ages of 18 to 80 years at the time of signing the informed consent document.
2. Understand and voluntarily sign an informed consent document prior to any study-related assessments/procedures are conducted.
3. Able to adhere to the study visit schedule and other protocol requirements.
4. Able to fluently speak and understand the local language
5. If female, is nonpregnant (negative pregnancy test results at the baseline/randomization visit) and nonlactating.
6. End-stage osteoarthritis patients planning to undergo primary total knee arthroplasty
7. BMI less than 40 kg/m²

Exclusion Criteria:

1. BMI greater than or equal to 40 kg/m²
2. History of known bleeding disorder

3. History of medical co-morbidity that may result in poor wound healing (ie. diabetes mellitus, peripheral vascular disease)
4. Patients <18 or >80 years of age
5. Patients who are prisoners
6. Mentally unable to sign informed consent
7. Has an uncontrolled illness that, in the opinion of the investigator, is likely to cause the patient to be withdrawn from the trial or would otherwise interfere with interpreting the results of the study.

Screening and Recruitment: Informed Consent

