- Cancer: Not related and unexpected within 10 working days from discovery/awareness

b) External Death:

Related/possibly related and unexpected – within 5 working days from discovery/awareness not related whether expected or unexpected – at time of continuing review related/possibly related and expected – at time of continuing review

c) ALL Deaths are also reported at time of continuing review using the AE summary log.

4. Non-serious Adverse events (Internal and External) that are both Related/Possibly related and unexpected are reported on the AE Summary Log at time of continuing review to assess trends.

5. An IRB staff (a qualified, licensed practitioner assigned to this function by the IRB chair and IRB Executive Director) reviews Adverse Event Reports to determine whether they represent Unanticipated Problem Involving Risks to Participants or Others. Events that are assessed, by either the IRB Staff or Investigator, to place subjects or others at a greater risk of harm than was previously known or recognized, or changes the risk/benefit ratio of the study, or requires a change in the protocol and/or consent document are referred to Full Board for review under Policy #70. Events that do not involve risk to Participants or Others or changes to the

informed consent or protocol do not require further review. Investigators are informed of the determination and the IRB file is updated.

6. The AE Summary Log is reviewed by the IRB at the time of continuing review to identify trends in frequency and severity which may impact subject safety.

This study is an Investigator Initiated research trial. Each study site will be considered its own regulatory sponsor and is responsible for internal data monitoring and any study reporting required by ClinicalTrials.gov.

Data Analysis:

Unless otherwise indicated, all testing of statistical significance will be two-sided, and a difference resulting in a p-value of less than or equal to 0.05 will be considered statistically significant. Also, after each analysis, General Linear Models (GLM) will be used to control for possible confounders, including BMI, gender, age and ethnicity.

References

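### Study Design rules out hypothesis testing, but Data Analysis sets a p ≤ 0.05 rule that reaches all four secondary endpoints with no error control across them

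*Combined protocol and SAP*

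**What the plan says.** The Study Design section names one primary endpoint, which "will be cosmesis observation using the modified Hollander scale", and four secondary endpoints: "wound closure time, patient satisfaction with wound appearance, wound related complications, cost comparison including time and materials". Straight after that list it states: "As a pilot study, hypothesis testing will not be performed".

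The follow-up text says "Post-operatively, patients will be assessed at clinic visits at 6 weeks and 3 months". The research procedures table schedules satisfaction and wound complications at both visits. Closure time is recorded once, during surgery.

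The Data Analysis section is two sentences long. Subject to exceptions indicated elsewhere, it makes every test two-sided. It adds that "a difference resulting in a p-value of less than or equal to 0.05 will be considered statistically significant". It then says that "after each analysis, General Linear Models (GLM) will be used to control for possible confounders", naming BMI, gender, age and ethnicity. It does not say which endpoints or visits are tested. It gives no order of testing, no division of alpha and no multiplicity procedure, and it does not call the secondary endpoints exploratory.

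**The concern.** The two sections cannot both be followed. One says that nothing will be tested; the other says how every test will be judged. An analyst working from Data Analysis alone would produce p-values for closure time, satisfaction, complications and cost, and would call any that reach 0.05 statistically significant.

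This matters because the protocol's background gives possible savings in operative time and cost as a reason to study the device in orthopaedics, and closure time and cost are secondary endpoints here. A single significant secondary result from 60 subjects could be quoted, or carried into the assumptions of a later trial, although the pilot disclaims testing and the rule does not limit the error rate over the set.

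**Working it through.** **Inputs from the documents.** Two-sided threshold 0.05 per test (Data Analysis). Four secondary endpoints (Study Design). Two follow-up visits, with satisfaction and complications assessed at each (follow-up text and research procedures table). 60 subjects randomized 1:1, so about 30 per arm.

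**Number of comparisons.** One per endpoint gives 4. Testing satisfaction and complications separately at each visit gives closure time 1 + cost 1 + satisfaction 2 + complications 2 = 6. The plan does not say that each visit is tested, so 6 is an inference. The primary endpoint is left out.

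**Assumptions not in the documents.** No true difference on any secondary endpoint; a common correlation ρ between test statistics of 0, 0.5 or 0.8; complication rates of 5% or 10%; Fisher's exact test for complications.

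**The plan's own figure.** The only stated figure is the 0.05 threshold, and one test returns it: 1 − 0.95 = 0.05. No family-wise rate is stated, and the sample size comes without power, effect size or standard deviation, so there is nothing else to reproduce.

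**Independent tests, either direction:** 1 − 0.95^k.
- k = 4: 1 − 0.95⁴ = 18.5%
- k = 6: 1 − 0.95⁶ = 26.5% (26.49% before rounding)

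**Independent tests, favouring the active arm.** A two-sided 0.05 test spends 0.025 in that direction, so the rate is 1 − 0.975^k.
- k = 4: 1 − 0.975⁴ = 9.6%
- k = 6: 1 − 0.975⁶ = 14.1%

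**Correlated tests.** With equal correlation ρ and standard normal x, the either-direction rate is 1 − E{[Φ((1.96 − √ρ·x)/√(1−ρ)) − Φ((−1.96 − √ρ·x)/√(1−ρ))]^k}. For one direction, drop the second Φ. Numerical integration gives:

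| Comparisons | ρ | Either direction | Favouring active arm |
|---|---|---|---|
| 4 | 0 | 18.5% | 9.6% |
| 4 | 0.5 | 15.6% | 7.8% |
| 4 | 0.8 | 11.4% | 5.7% |
| 6 | 0 | 26.5% | 14.1% |
| 6 | 0.5 | 20.7% | 10.4% |
| 6 | 0.8 | 13.9% | 6.9% |

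**Sparse complications.** With 30 per arm, the true level of Fisher's exact test at nominal 0.05 is 0.0015 at a 5% event rate and 0.0094 at 10%. For independent tests, either direction:
- Four comparisons: 1 − 0.95³ × (1 − 0.0015) = 14.4%; 1 − 0.95³ × (1 − 0.0094) = 15.1%
- Six comparisons: 1 − 0.95⁴ × (1 − 0.0015)² = 18.8%; 1 − 0.95⁴ × (1 − 0.0094)² = 20.1%

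These figures count unadjusted p-values only. The adjusted model after each analysis could double the secondary p-values to 12, and the plan does not say which of each pair governs. Accepting either would raise the rates, but the plan does not say that either suffices, so no such figure is used.

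**The case against.** The strongest reply is that the Study Design statement already settles the matter: if it governs, no secondary endpoint is tested and no inflation arises. The Data Analysis text is generic, names no endpoint, and reserves exceptions indicated elsewhere, which could be read as deferring to Study Design. This stands in part. The contradiction is the first defect, and multiplicity follows only if the Data Analysis rule is followed. But Data Analysis does not say that it defers, and on that reading its rule and its adjusted models would apply to nothing. The documents do not settle which section prevails.

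Second, the assumption of no true difference is doubtful for time and cost. The arms use different materials by design, and cost includes both time and materials, so it overlaps with closure time. If those two endpoints truly differ, only satisfaction and complications can give false positives. With independent tests and Fisher's test as above, the either-direction rate is then 1 − 0.95 × (1 − 0.0015) = 5.1% to 1 − 0.95 × (1 − 0.0094) = 5.9% at one visit. At two visits it is 1 − 0.95² × (1 − 0.0015)² = 10.0% to 1 − 0.95² × (1 − 0.0094)² = 11.4%. This stands as a limit on the size.

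Third, unadjusted secondary endpoints are common in a small pilot that makes no confirmatory claim. That is fair, and is a reason to report estimates rather than add a formal multiplicity procedure. It does not justify a rule that labels those results statistically significant.

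A reader might also infer that the larger percentages are the chance of a false *benefit* of the new closure. They are not: they include results favouring staples, and the chance in the active arm's favour is roughly half as large. Nor do the documents say that a significant secondary result would be treated as established, only that it would be considered statistically significant.

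**Conclusion.** The point holds as an inconsistency with a measurable consequence. Study Design disclaims testing, while Data Analysis prescribes it without excluding the secondary endpoints or controlling error across them.

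If Data Analysis is followed and there are no true differences, at least one false significant secondary result in either direction has a probability of about 11% to 26% (four to six full-alpha comparisons, correlation 0.8 to 0). For a result favouring the active arm it is about 6% to 14%, against 2.5% for one test in that direction. Sparse complications under Fisher's test bring the independent-test, either-direction figures to about 14% to 20%. The correlations, event rates, choice of test and separate testing of visits are assumptions, and true differences in time or cost would lower the figures further. If Study Design governs, the inflation does not arise, but the Data Analysis text still needs correcting. This is a cheap improvement, not a flaw that undermines the pilot.

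**What to change.** Reconcile Data Analysis with Study Design by lifting the significance rule from the secondary endpoints. Suggested wording:

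> Closure time, VAS satisfaction (6 weeks and 3 months), wound complications (6 weeks and 3 months) and cost are exploratory. Each will be reported as a between-arm difference with a 95% confidence interval, unadjusted for multiplicity, and will not be described as statistically significant.

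This takes one or two sentences and needs no new data, patients or procedures. The small downside is that an isolated secondary p ≤ 0.05 can no longer be reported as a significant finding, which agrees with what Study Design already says about testing.

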Patients will be randomized to either arm of the study as follows: sealed envelopes in a random order will be used to place study participants in either the active arm or in the control arm of the study. Patients will be randomized in a one to one ratio. At the commencement of each arthroplasty, a random envelope will be drawn which dictated the type of suture to be used, thus blinding the patients to the type of suture they received.

Research Procedure:

A medial parapatellar approach will be performed. All closures will be performed in 3 layers, with the knee in approximately 90° of flexion to minimize potential imbrication of the capsule. For the traditional closure (control group), the arthrotomy (deep layer) is repaired using number 1 Vicryl followed by closure of the intermediate layer with a 2-0 Vicryl and the skin will be closed with staples (Standard of care).

For the active arm of the study, the arthrotomy (deep layer) is repaired using number 1 Vicryl, the subcutaneous layer will be then closed with simple interrupted knots using number 2-0 braided absorbable sutures (Vicryl), followed by closure of the subcutaneous layer using a STRATAFIX Spiral Knotless Tissue Control Device in addition to DERMABOND PRINEO (Ethicon, Johnson and Johnson, Somerville, New Jersey) system for dermal closure. (See table 3).

Closure with the bidirectional barbed suture involves starting at the midpoint of the wound and proceeded simultaneously both proximally and distally to the ends. At the ends of the wounds, the suture is backstitched at this subcuticular level (2-3 throws) toward the midpoint for further reinforcement before bringing the needle out through the skin; the suture is then cut flush with the skin tissue at its free end. With each throw, the leading end of the suture is pulled with only enough tension to engage the barbs with the surrounding tissue, thereby locking the wound edges into approximation. As with the traditional closure and in concordance with our routine protocol, skin will be closed with staples.

Table 2: Suture Type for Closure Following Total Knee Arthroplasty.		
Layer	Control Group	Active Group
Capsule	Vicryl #1 (J947H#1)	Vicryl #1 (J947H#1)
Subcutaneous	Vicryl 2.0 (J945H 2-0)	Vicryl 2.0 (J945H 2-0)
Subcuticular	Staples	STRATIFIX Spiral Knotless tissue control device (undyed)
Skin		DERMABOND PRINEO

Patient Protection:

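### Cosmesis and VAS are scored at two visits, but the named GLM has no visit structure; a mixed model on both visits would be a cheap improvement

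*Combined protocol and SAP*

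**What the plan says.** - **Endpoint.** Under Study Design, the primary endpoint "will be cosmesis observation using the modified Hollander scale". Patient satisfaction with wound appearance is a secondary endpoint, scored on a VAS.
- **Visits.** The follow-up paragraph states: "Post-operatively, patients will be assessed at clinic visits at 6 weeks and 3 months". The research procedures table marks both instruments at both visits and neither before surgery.
- **Score.** Table 1 lists six items scored 0 or 1, with 1 the better result. No rule for combining them is given; a sum would run from 0 to 6.
- **Size.** The Sample heading gives "60 subjects for a pilot study", and the randomisation section adds "Patients will be randomized in a one to one ratio", which means 30 per arm.
- **Model.** The Data Analysis section is two sentences. The first sets two-sided testing at 0.05. The second says that, after each analysis, "General Linear Models (GLM) will be used to control for possible confounders", listing BMI, gender, age and ethnicity.

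The documents do not say which visit is primary, whether the visits are analysed separately or together, how scores from one patient are related in the model, or what happens when a visit is missed.

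**The concern.** Each patient is due to give two related scores on each instrument, and the model is described as if there were one. The most natural use of a GLM here is a separate fit at each visit. A patient seen at 6 weeks but not at 3 months then contributes nothing to the 3-month estimate, although the 6-week score says something about the missing one.

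Two things are at stake. The first is precision, which matters in a trial of 60. The second is bias: if patients with poor early wounds miss 3 months at different rates in the two arms, the patients who remain are no longer comparable.

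**Working it through.** **Inputs from the documents.** 60 patients, 1:1, so n = 30 per arm; two visits. The sample size comes with no effect size, SD, power or dropout, so there is no figure of the plan's own to reproduce.

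**Assumed inputs.** Share missing at 3 months m = 10–20%, with everyone seen at 6 weeks; correlation between visits ρ = 0.3–0.8; equal variance σ² at both visits. None of these is in the documents.

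**Step 1: precision.** A 3-month-only GLM uses n₁ = n(1 − m) patients per arm, with variance σ²/n₁ for each arm mean. A model that also uses the 6-week scores has, in large samples, variance

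σ²(1 − ρ²)/n₁ + σ²ρ²/n = (σ²/n₁)(1 − mρ²).

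The proportional reduction in variance is therefore mρ², and the effective number per arm is n₁/(1 − mρ²).

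| m | ρ | Patients used by the GLM, per arm | Variance reduction mρ² | Effective n per arm |
|---|---|---|---|---|
| 10% | 0.3 | 27.0 | 0.9% | 27.2 |
| 10% | 0.5 | 27.0 | 2.5% | 27.7 |
| 10% | 0.8 | 27.0 | 6.4% | 28.8 |
| 20% | 0.3 | 24.0 | 1.8% | 24.4 |
| 20% | 0.5 | 24.0 | 5.0% | 25.3 |
| 20% | 0.8 | 24.0 | 12.8% | 27.5 |

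Confidence-interval width scales with √(1 − mρ²). The interval is thus between 0.5% (√0.991 = 0.9955) and 6.6% (√0.872 = 0.934) narrower. At m = 0 the reduction is zero. A simulation of 20,000 trials with 30 per arm and 15% missing gave reductions of 3.4% at ρ = 0.5 and 9.9% at ρ = 0.8; the formula gives 3.75% and 9.6%.

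**Step 2: bias under one assumed dropout pattern.** Suppose there is no true difference. In the active arm, patients in the bottom third of 6-week scores miss 3 months 40% of the time and the others 5%; in the control arm everyone misses 15% of the time. Take scores as normal with SD 1.

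- Mean 6-week score is −1.091 in the bottom third and +0.545 in the rest.
- Share of the active arm seen at 3 months: (1/3)(0.60) + (2/3)(0.95) = 0.200 + 0.633 = 0.833.
- Mean 6-week score of those seen: (0.200 × −1.091 + 0.633 × 0.545)/0.833 = 0.153 SD, against 0 in the control arm.
- Carried to 3 months by ρ: 0.5 × 0.153 = 0.076 SD, and 0.8 × 0.153 = 0.122 SD.

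The bias favours the active arm, because a higher Hollander score is better. Simulation gave 0.073 and 0.123 SD for the 3-month-only difference. Using the 6-week score gave −0.003 and 0.000 SD.

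For scale, with about 25 and 25.5 patients seen per arm, the standard error of the difference is √(1/25 + 1/25.5) = 0.281 SD. The bias is about 0.27 to 0.43 of one standard error.

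The result depends on what counts as a low score. The bottom quarter gives 0.064–0.103 SD and the bottom half 0.090–0.144 SD over the same correlations.

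**The case against.** **A stronger reading does not stand.** A reader might infer that a GLM cannot handle two scores per patient, so that it must either drop patients or count them twice. The documents do not support this. Nothing in them proposes stacking the two visits as independent records. A GLM at one visit, or on each patient's mean of the two visits, counts nobody twice; in simulation with complete data both held 4.9–5.0% false positives at a nominal 5%. Stacking would raise that rate (about 11% at ρ = 0.5) only for a single arm effect pooled over visits. The 3-month contrast from a stacked model with an arm-by-visit term stayed at about 5%.

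**The gain is small and rests on assumptions.** This stands. The documents give no dropout or correlation, and inclusion criterion 3 asks that patients be able to keep the visit schedule, so few visits may be missed. The dropout pattern in the bias example was chosen to show the mechanism; nothing in the documents suggests that dropout differs by arm.

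**The GLM is only an adjustment step.** This also stands. The section applies it after each analysis and does not name the analysis that comes first. Changing the GLM alone would leave that gap, so the text should say that the mixed model is the analysis for these two scores.

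**The pilot may not test at all.** Study Design says "As a pilot study, hypothesis testing will not be performed", while Data Analysis sets a significance rule. The two must be reconciled, but the point does not depend on the outcome: it concerns the estimate and its interval.

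**Conclusion.** This is a cheap improvement. A visit-by-visit GLM is valid with complete data and there is then essentially nothing to gain. With 10–20% missing at 3 months and a correlation of 0.3–0.8, the variance of the 3-month difference falls by about 1–13%. Under the dropout pattern worked through above, with low scorers defined as the bottom third and a correlation of 0.5–0.8, a bias of about 0.07–0.12 SD is largely removed, provided that missingness depends only on observed scores. Those rates and correlations are illustrations, since the documents supply none. The unnamed primary visit and the absent rule for missed visits are gaps in specification that the same edit can close.

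**What to change.** For the Hollander and VAS scores, replace the adjusted GLM in Data Analysis with a linear mixed model:

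- terms for arm, visit and arm-by-visit, plus BMI, gender, age and ethnicity;
- unstructured covariance between a patient's two scores;
- every randomised patient with at least one score, in the allocated arm;
- the arm difference with a 95% CI at each visit, and one visit named in advance as primary.

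The arm-by-visit term keeps a separate difference at each visit, so early and late scars are not averaged. Naming one visit also settles which result leads: if both were tested at 0.05, the chance of at least one false positive would be about 7–9.5% for correlations of 0.9 down to 0.3.

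The cost is a few lines of text and a standard model, with no new data. There are limits. The model assumes that missed visits are explained by observed data, it cannot include a patient with neither score, and, like the GLM, it treats a bounded score as continuous. The scoring rule for the Hollander items should be stated at the same time.
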